16.4 Abbreviations

AE	Adverse Event
AIS	Acute Ischemic Stroke
CFR	Code of Federal Regulations
CRF	Case Report Form
DNA	Deoxyribonucleic Acid
eCRF	Electronic Case Report Form
EDC	Electronic Data Capture
EN	European Norm
ENT	Embolization to Uninvolved or New Territories
FDA	Food and Drug Administration
FU	Follow-Up
GCP	Good Clinical Practices
GCS	Glasgow Coma Score
I/E	Inclusion/Exclusion
IA	Intra-Arterial
ICF	Informed Consent Form
IFU	Instructions For Use
IRB	Institutional Review Board
I.S.	Irish Standard
ISO	International Organization for Standardization
ITT	Intent To Treat
IV	Intravenous
LAR	Legally Authorized Representative
LTFU	Lost to Follow-Up
MIS	Minimally Invasive Surgery
mRS	Modified Rankin Scale
MT	Mechanical Thrombectomy
mTICI	Modified Treatment in Cerebral Ischemia
NIHSS	National Institute of Health Stroke Scale
PP	Per Protocol
RNA	Ribonucleic Acid
SAE	Serious Adverse Event
sICH	Symptomatic Intracerebral Hemorrhage; defined as 24 hour CT evidence of an ECASS defined ICH and a 4-point or more worsening of the NIHSS score
SNPs	Single Nucleotide Polymorphism
tPA	Tissue Plasminogen Activator
US	United States

16.5 Definitions

16.5.3 Adverse Event (AE): any untoward medical occurrence, unintended disease or injury, or untoward clinical signs (including abnormal laboratory findings) in participants, users or other persons, whether or not related to the study device and whether anticipated or unanticipated.

- **Serious Adverse Event (SAE)** An adverse event is serious if the event led to the following:
 - Death
 - Serious deterioration in the health of the participant that resulted in any of the following:
 - Life-threatening illness or injury
 - Permanent impairment of a body structure or a body function
 - Hospitalization or prolongation of patient hospitalization
 - Medical or surgical intervention to prevent life-threatening illness or injury or permanent impairment to a body structure or a body function
 - Fetal distress, fetal death or a congenital physical or mental impairment or birth defect
- **Unanticipated Adverse Device Event (UADE):** An unanticipated adverse device effect is any serious adverse effect on health or safety or any life-threatening problem or death caused by, or associated with, a device, if that effect, problem, or death was not previously identified in nature, severity, or degree of incidence in the protocol, IFU, or risk analysis. Unanticipated adverse device effect also includes any other unanticipated serious problem associated with a device that relates to the rights, safety, or welfare of participants.
- **Relationship to the Device**
 - **Definite:** The temporal sequence is relevant and the event abates upon study device application completion/removal, or reappearance of the event on repeat study device application.
 - **Probable:** The temporal sequence is relevant or the AE abates upon study device application completion/removal or the AE cannot be reasonably explained by the participant's condition or comorbidities. The AE is related or most likely associated with the study device.
 - **Possible:** The temporal sequence between the study device and the AE is such that the relationship is not unlikely or there is no contradicting evidence that can reasonably explain the participant's condition. There is a possibility of a relationship between the AE and the study device.
 - **Unrelated:** The AE is not associated with the device. There is no relation between the AE and the study device.

Similar grading will be used for assessing the relationship to index procedure.

INSIGHT: Investigation of Clot in Ischemic Stroke and Hematoma Evacuation

STATISTICAL ANALYSIS PLAN

CLP-15131

Version 3.0

Sponsor

Penumbra, Inc.
[name]
[name]
USA

Contents

1. Overview	3
2. Study objectives	3
2.1 Primary Objectives	3
2.2 Secondary Objectives	4
3. Sample size.....	4
4. Interim analysis.....	4
5. General Statistical methods.....	4
6. Patient Disposition	4
6.1 Enrolled	4
6.2 Completed.....	5
6.3 Early Termination.....	5
7. Definition of Analysis Population	5
8. Statistical Analysis	5
9. Analysis of adverse events.....	6
10. Subgroup analysis.....	6
11. Pooling across centers	7
12. Lost to follow-up and missing data	7
13. Central Core and Pathophysiology Lab.....	8
14. Changes to planned analysis	8
15. References	8
16. Revision History.....	8

1. Overview

This is a prospective, multicenter, registry for the collection and analysis of specimen collected from ischemic stroke thrombectomy procedures and minimally invasive interventions for intracranial hematoma evacuation utilizing the Penumbra Aspiration Pump. The aim of the study is to collect and analyze specimen via histology, RNA sequencing, Single Nucleotide Polymorphisms (SNPs), and proteomic analysis. This will then be correlated to comprehensive data relating to patient's clinical presentation, hospital course, and length of hospital stay. Patients eligible for thrombectomy or minimally invasive surgery, who meet the inclusion and none of the exclusion criteria will be considered for enrollment. Treatment will be per site routine practice, using FDA cleared devices. Patients will be considered enrolled upon signed informed consent and specimen collection. Up to 400 patients from up to 30 sites in the United States will be enrolled into this registry. Each site will be limited to a maximum enrollment of 60 subjects (approximately 15% of the total enrolled). It is anticipated that enrollment will take approximately 2 years. Each patient will be in the registry for up to 90 days from enrollment to last follow-up. Data for each subject will be collected at the time of enrollment, discharge or 7days (whichever comes first) and 90 Days (optional) follow-up.

2. Study objectives

This study will examine whether clot composition, genetic, and proteomic variables can provide insight into thrombus etiology and/or have impact on clinical outcomes in patients with outwardly similar initial presentations.

2.1 Primary Objectives

The aim of the study is to collect and analyze specimen from, ischemic stroke patients undergoing thrombectomy procedures, and from patients undergoing minimally invasive surgery for intracranial hematoma evacuation. Clot and blood specimen will be analyzed via histology, RNA

sequencing, Single Nucleotide Polymorphisms (SNPs), and proteomic analysis.

2.2 Secondary Objectives

To prospectively collect and correlate data relating patient's clinical presentation, hospital course, and length of hospital stay to specimen histology, RNA sequencing, SNPs, and proteomic analysis.

3. Sample size

Due to the descriptive nature of this registry with no formal statistical hypothesis test, sample size calculations were not performed. Up to 400 subjects will be enrolled in the registry.

4. Interim analysis

No interim analyses are planned for the purpose of stopping the study early. Interim analysis may be performed for publication of registry results. No adjustments will be made to the confidence bounds for the final analysis.

5. General Statistical methods

No formal statistical testing is planned for this study. All statistical analyses will be descriptive in nature. Descriptive statistics will include the number of observations, mean, median, standard deviation, inter-quartile range, minimum and maximum for continuous variables and counts and percentages for discrete variables. All confidence intervals presented will be two-sided. Analyses will be conducted using SAS (SAS Institute, Cary, NC).

6. Patient Disposition

6.1 Enrolled

Patients will be considered enrolled upon signed informed consent and specimen collection.

6.2 Completed

All patients who were enrolled and completed either the Discharge/7 Day or 90 Day Follow-Up visit or were known to have died prior to 90 days are considered completed.

6.3 Early Termination

Subjects who were enrolled but did not complete any follow-up visits and were not known to have died.

7. Definition of Analysis Population

7.1 Intent to treat

All enrolled subjects will be analyzed under the intent-to-treat (ITT) principle.

8. Statistical Analysis

This plan is limited to the analysis of clinical data and specimen histology. The number of patients enrolled, patients completing the study, patients not completing the study, and patients completing the optional 90 Day Follow-Up visit will be summarized. Clot characteristics, such as clot location, clot organization, composition, clot etiology, clot dimensions, and specimen histology, will be summarized using descriptive statistics¹. Baseline data including, but not limited to demographics, clinical, procedural, and imaging characteristics from ischemic stroke patients and patients eligible for minimally invasive hematoma evacuation will be summarized using descriptive statistics. Exploratory multivariate analyses will be conducted. Results collected at multiple

visits will be summarized at each visit for which they are collected as described in Schedule of Assessments Table. Summaries for all measures will include all observed data for each visit.

9. Analysis of adverse events

Serious adverse events will be collected in this registry on patients treated with any of the RED reperfusion catheters from procedure through discharge or 7 days post-procedure. Serious device related adverse events, serious procedure related adverse events will be summarized by showing the number and percent of subjects which report the event.

Other safety events collected on the case report form through 7 days post procedure will include symptomatic ICH at 24 hours, and symptomatic embolization of unininvolved or new territory (ENT)

All information pertaining to adverse events noted during the study will be listed by subject, detailing category, date of onset, date of resolution, relation to device or procedure and seriousness. The onset of serious adverse events will be shown relative (in number of days) to the day of procedure.

10. Subgroup analysis

To evaluate the impact of baseline conditions on procedural and clinical outcomes as well as clot characteristics, subgroup analyses will be performed for procedural outcomes of mTICI score, clinical outcomes of mortality at 90 days, NIHSS score at discharge and the proportion of patients that achieve mRS of 0 to 2 at 90 days (if available) and clot characteristics of gross appearance, clot sign, size, weight, volume and histology.

The subgroups below will be used for these analyses:

- *Stroke type (Ischemic or Hemorrhagic)*
- *Location of Intracerebral Hemorrhage (Deep or Lobar)*
- *Age (Less than 65 or 65 and older)*
- *Gender (Male or Female)*

- *Race (White, Black, Asian or Any other)*
- *Ethnicity (Hispanic or Non-Hispanic)*
- *Smoking status (Current, Former or Never smoked)*
- *Covid status (Active, Previous or No History of COVID)*
- *Time of stroke onset to procedure. (6 or less hours or More than 6hrs in Ischemic subgroup only)*

Descriptive statistics and 95% confidence intervals will be presented for each subgroup and the difference between subgroups. Notable differences between subgroups will be further evaluated using additional covariates and multivariate modeling to describe relationships between subgroups and clinical outcomes. These analyses will be performed in the Intent-to-Treat population given adequate numbers for robust analysis.

11. Pooling across centers

Analyses will be presented using data pooled across centers. Descriptive statistics for key variables such as age, baseline NIHSS, IV rtPA administration, stroke type, target vessel location, mTICI, and mRS will be presented to assess any potential site effects. If there is evidence of site heterogeneity, additional analyses will be performed to determine confounding factors influencing site and clinical outcomes. Appropriate stratified and modeling techniques, including contingency tables, logistic regression, and random effects will be used to assess differences between study centers to justify pooling data across centers. To avoid the influence of small enrolling sites on contingency tables, low enrolling sites will be removed as a sensitivity test for contingency table analyses.

12. Lost to follow-up and missing data

Every effort will be made to keep all missing data to a minimum. Patient discontinuation rates will be tabulated by the reason for early termination. Any

loss of viable or insufficient sample will be noted. The primary analysis will be data as observed.

13. Central Core and Pathophysiology Lab

In addition to the analysis detailed above, up to three independent laboratories will follow the Study Core Lab Charter to analyze collected samples via histology, proteomics, transcriptomics, and genomics.

14. Changes to planned analysis

All changes to the statistical analysis plan (SAP) will be documented in a revised SAP or in the clinical trial report.

15. References

1. Agresti (2014) Categorical Data Analysis. John Wiley & Sons: New Jersey

16. Revision History

Version	Description of Changes	Prepared by
1	Initial Release	
2	Revised to reflect increased enrollment of updated protocol. Clarified subgroup analysis categories. Added section 16 Revision History	
3	Revised Section 9: Analysis of adverse event (AE) section as we are collecting AE for the RED subgroup in Protocol E

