7.5.1 Adverse Events

Serious Adverse Events (AE) will be collected in this registry on patients treated with any of the RED reperfusion catheters from procedure through discharge. Serious device related events, serious procedure related adverse events, symptomatic ICH at 24 hours, device deficiencies leading to adverse events, and symptomatic embolization of new territory (ENT) and will be collected on the case report form through 7 days post procedure. No additional risk is associated with specimen collection.

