10.6 Definition of Analysis Population

All enrolled patients will be analyzed under the intent-to-treat (ITT) principle.

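### Protocol 7.5.1 and SAP 9 limit SAE collection to RED-treated patients, protocol 5.5, 5.6 and Table 1 do not, and SAP 9 names no denominator for its SAE percentages

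*Combined protocol and SAP*

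**What the plan says.** **Who is under collection.** The opening sentence of protocol 7.5.1 reads: "Serious Adverse Events (AE) will be collected in this registry on patients treated with any of the RED reperfusion catheters from procedure through discharge". SAP 9 has the same limit: "Serious adverse events will be collected in this registry on patients treated with any of the RED reperfusion catheters". Protocol 5.5 (Procedure) and 5.6 (Discharge or 7 Days) list SAE collection with no RED limit. Table 1 has an SAE row whose footnote 7 restricts event types and time, not patients.

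**Which events.** The second sentence of 7.5.1 puts device related and procedure related serious events together with symptomatic ICH, symptomatic embolization of new territory (ENT) and certain device deficiencies, and does not repeat the RED limit. SAP 9 places the related SAEs directly after its RED sentence. ICH and ENT come in a separate paragraph: "Other safety events collected on the case report form through 7 days post procedure will include symptomatic ICH at 24 hours".

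**How reported.** Under SAP 9, related SAEs are "summarized by showing the number and percent of subjects which report the event". Adverse event information is also to be listed subject by subject.

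**Population.** SAP 7.1: "All enrolled subjects will be analyzed under the intent-to-treat (ITT) principle". Protocol 10.6: "All enrolled patients will be analyzed under the intent-to-treat (ITT) principle". SAP 8 adds "Summaries for all measures will include all observed data for each visit", and SAP 12 adds "The primary analysis will be data as observed". Neither document defines a RED-treated population.

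**The concern.** A site that follows 7.5.1 would record SAEs for RED-treated patients only. A site that follows the visit lists and Table 1 would record them for everyone. The data would then come from mixed collection rules, and the analyst would have no written basis for choosing a denominator.

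RED use is not an eligibility criterion. Protocol 4.1 admits patients treated with the Penumbra System for ischemic stroke and patients treated with the Artemis device for hematoma evacuation. The enrolled population can therefore include many patients outside the RED limit. If they were never under SAE collection but stay in the denominator, they count as event-free without having been assessed, and the reported percentage is too low.

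**Working it through.** The plan states no SAE rate, RED share or safety sample size, so it has no figure to reproduce. The check is a comparison of passages followed by an illustration.

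**1. Passages side by side**

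| Place | Patients | Events | Window |
|---|---|---|---|
| Protocol 5.5, 5.6 | no RED limit | SAEs | at procedure; at discharge or day 7 |
| Table 1 footnote 7 | no RED limit | device related, procedure related, symptomatic ICH, ENT | 7 days |
| Protocol 7.5.1, first sentence | RED-treated | SAEs | to discharge |
| Protocol 7.5.1, second sentence | not stated | related serious events, ICH, ENT, device deficiencies leading to adverse events | 7 days |
| SAP 9, opening | RED-treated | SAEs; related SAEs follow directly | discharge or 7 days |
| SAP 9, second paragraph | not stated | ICH, ENT | 7 days |

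Protocol 5.5, 5.6 and Table 1 do mark other items as applying only to ischemic stroke or only to surgery patients, so a RED marker could have been shown there. Section 7.5.1 can be read as two tiers: all SAEs in RED-treated patients to discharge, and a listed set through 7 days. That does not settle the scope, because related SAEs fall in the second tier in 7.5.1 but follow the RED sentence in SAP 9.

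The windows give different lengths. For an assumed stay of 12 days, collection to discharge runs 12 − 7 = 5 days beyond a 7-day window. For an assumed discharge on day 3, it stops 7 − 3 = 4 days short of one.

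**2. Effect of the denominator if collection is RED-only**

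Inputs: N = 400 enrolled (the maximum in SAP 3). Assumed, because the documents do not give them: a true rate of 10% among RED-treated patients, and 100, 200 or 300 RED-treated patients.

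Reported rate over all enrolled = (rate among RED-treated) × (RED-treated / 400). Intervals are exact (Clopper-Pearson) 95%.

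| RED-treated | With event | % of RED-treated | % of all enrolled |
|---|---|---|---|
| 100 | 10 | 10.0 (4.9–17.6) | 10/400 = 2.5 (1.2–4.5) |
| 200 | 20 | 10.0 (6.2–15.0) | 20/400 = 5.0 (3.1–7.6) |
| 300 | 30 | 10.0 (6.8–14.0) | 30/400 = 7.5 (5.1–10.5) |
| 400 | 40 | 10.0 (7.2–13.4) | 40/400 = 10.0 (7.2–13.4) |

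The ratio of the two percentages is the RED share, whatever the event rate. At an assumed 5% and 200 RED-treated patients, 10/400 = 2.5%. At an assumed 20%, 40/400 = 10%.

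**3. The reverse case**

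Suppose all 400 are under collection but only 200 RED-treated patients are summarised. At 10% throughout, 40 patients have an event, and 20 of them fall outside the percentage. They would still appear in the by-subject listing in SAP 9.

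**The case against.** The best defence is that the intent is clear enough. The version 3 entry in the SAP revision history says that adverse events are collected for the RED subgroup. Section 7.5.1 is the dedicated reporting section and names the patients. Protocol 5.5 is permissive about what the CRF captures, and a visit list that does not repeat a limit stated elsewhere is not a direct contradiction. The observed-data statements in SAP 8 and 12 also leave room for a RED-treated denominator, and no passage says that unassessed patients are to be counted as event-free.

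Much of this stands. RED-only collection is the likelier intent, and the dilution is conditional. But the revision note does not amend protocol 5.5, 5.6 or Table 1, which sites work from. It does not explain why related SAEs are grouped differently, and it names no denominator. The observed-data statements allow a RED-treated denominator without specifying one, while the one defined population points to all enrolled.

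Three stronger readings are tempting but not supported:

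- **Safety data would be lost if only RED-treated patients are summarised.** They would be missing from a percentage, but SAP 9 still lists them by subject.
- **A 7-day SAE rate will miss events after early discharge.** SAP 9 does not label the related-SAE percentage as a 7-day rate. Protocol 7.5.1 asks for the listed events through 7 days without tying this to a visit, so the lack of a later scheduled check does not show that events go unrecorded.
- **ICH and ENT percentages lack a denominator.** SAP 9 says that these events are collected but plans no percentage for either.

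**Conclusion.** The point holds as a minor one. Protocol 5.5, 5.6, Table 1 footnote 7, 7.5.1 and SAP 9 do not agree on the patients or the window for SAE collection, and they leave unclear whether related SAEs fall under the RED limit. SAP 9 does not say what its SAE percentages are percentages of.

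The possible understatement equals the RED share: a factor of 0.25, 0.5 or 0.75 at assumed shares of 25, 50 or 75%. It arises only if collection is RED-only and all enrolled patients are the denominator. It disappears if everyone is under collection, if the share is 100%, or if the denominator is RED-treated patients. The RED share, event rates and lengths of stay are all assumptions, so the documents do not show that any rate will in fact be diluted.

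The consequence is limited to descriptive safety reporting. No objective, test or sample size depends on it.

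**What to change.** 1. Reconcile protocol 5.5, 5.6, Table 1 footnote 7 and 7.5.1 with SAP 9 on which patients, which events and which window are under SAE collection. Say explicitly whether related SAEs, ICH and ENT are limited to RED-treated patients.
2. In SAP 9, take as denominator of each reported safety percentage exactly the patients under collection for that event, and do the same for ICH and ENT if percentages are reported for them. State that this rule governs safety summaries over the general ITT statement in SAP 7.1. If the reconciled scope is all patients, the denominator is all enrolled and nothing changes.
3. Once the windows are reconciled, state in SAP 9 the observation window for each rate.

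The cost is wording in the SAP and a protocol clarification. The CRF is not among the documents; a collection-status field is needed only if RED use is not already recorded. Under RED-only collection the denominator is smaller, and the reported rate is higher with a wider interval: in the illustration, 10.0% (6.2–15.0) in place of 5.0% (3.1–7.6).

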5.6 Discharge or 7 Days (whichever occurs first)

The following assessments will be performed per site routine practice at discharge or 7 Days post procedure:

- National Institutes of Health Stroke Scale (NIHSS)
- Modified Rankin Scale (mRS)
- Glasgow Coma Score (GCS) – (MIS only)
- SAE collection

5.7 90 Day Follow-Up ±14 Days (Optional phone visit)

The following assessment will be performed per site routine practice at this optional phone visit:

- Modified Rankin Scale (mRS)

Table 1: Schedule of Assessments

ACTIVITY	Baseline Evaluation	Procedure	Discharge or 7 Days ⁶	90 Day Follow-Up ¹ (±14 Days)
Informed Consent²	X			
Medical History	X			
Demographics	X			
Medication Review	X	X		
Clot Retrieval		X		
Blood Sample Collection		X		
Hematoma Volume³		X		
NIHSS	X		X	
mTICI⁴		X		
mRS	X ⁵		X	X
GCS³	X		X	
Serious Adverse Events⁷		X	X	

¹Optional Visit (conducted by phone)

² May be obtained up to 1 calendar day post-procedure and must be obtained prior to shipment of samples

³ Minimally invasive surgery / hematoma evacuation patients only

⁴ Ischemic stroke patients from digital subtracted angiography

⁵ Historical (pre-stroke)

⁶ Whichever occurs first

⁷ The following SAEs will be collected through 7 days post procedure: Device related events, procedural related events, Symptomatic ICH (sICH) at 24 hours, symptomatic embolization of new territory (ENT) at end of procedure

6. Specimen Collection and Shipment

All specimen should be placed within the provided collection tube(s) then securely packaged in the specimen collection kit provided, and shipped to the Core Lab(s) as quickly as possible, but no later than 72 hours post procedure and after informed consent is obtained.

The study sponsor will provide specimen kits, comprised of the following components:

- Mini Sample collection tube(s) for the clot
- Sealable plastic biohazard bags
- Absorbent material
- Paraffin tape for mini sample collection tubes(s)
- Purple collection tubes for blood samples (x2)
- Return packaging for specimen shipment to the Core Lab(s)
- UN 3373, Biological substances, Category B label
- Instructions for specimen collection, packing and shipping the specimen kit

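### Protocol 7.5.1, Table 1 footnote 7 and SAP 9 disagree on which serious adverse events are collected, in whom and for how long, and SAP 9 prespecifies no any-SAE rate and no explicit sICH or ENT row

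*Combined protocol and SAP*

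**What the plan says.** Several passages govern SAE collection.

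- Protocol 7.5.1, first sentence: "Serious Adverse Events (AE) will be collected in this registry on patients treated with any of the RED reperfusion catheters from procedure through discharge". It sets no relationship condition.
- Protocol 7.5.1, second sentence: a five-item list through 7 days, which opens "Serious device related events, serious procedure related adverse events, symptomatic ICH at 24 hours, device deficiencies leading to adverse events" and ends with symptomatic ENT. This sentence has no RED limit.
- Protocol Table 1, footnote 7: "The following SAEs will be collected through 7 days post procedure: Device related events, procedural related events, Symptomatic ICH (sICH) at 24 hours", with symptomatic ENT at the end of the procedure as the fourth item. It has no RED limit and no device deficiencies.
- Protocol 5.5 and 5.6 name SAE collection without qualification.
- SAP 9: "Serious adverse events will be collected in this registry on patients treated with any of the RED reperfusion catheters", with the window "from procedure through discharge or 7 days post-procedure".

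On tabulation, SAP 9 says: "Serious device related adverse events, serious procedure related adverse events will be summarized by showing the number and percent of subjects". For the other named events it says: "Other safety events collected on the case report form through 7 days post procedure will include symptomatic ICH at 24 hours", and adds symptomatic ENT. No summary statistic is attached to either. A by-subject listing of noted adverse events follows, which includes relation to device or procedure and seriousness.

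**The concern.** Sites that work from the schedule of assessments and sites that work from 7.5.1 can enter different events for the same kind of patient. An event that was never entered cannot be recovered at analysis. Protocol 7.5.3 asks for deviation reports only on eligibility and consent, so an omitted SAE would not surface there.

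The only explicit safety percentages in SAP 9 rest on relatedness calls, and no event review is described: protocol section 11 covers specimen laboratories only. In acute stroke, complications of the disease and of the procedure can look alike. A rate that does not depend on that call is the natural companion to the two that do, and SAP 9 does not prespecify one. The revision history shows that SAP version 3 was issued to revise this section for RED patients, so the output is a deliberate one.

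**Working it through.** The documents give no SAE rate, no number of RED patients and no planned figure on this point, so there is nothing to reproduce. The check is a comparison of the texts.

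**Step 1: scope, population and window**

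| Source | Events | Patients | Window |
|---|---|---|---|
| Protocol 7.5.1, sentence 1 | SAEs, no filter | RED-treated | Through discharge |
| Protocol 7.5.1, sentence 2 | 5 listed items | No limit stated | Through 7 days |
| Table 1, footnote 7 | 4 listed items | No limit stated | Through 7 days |
| SAP 9, sentence 1 | SAEs, no filter | RED-treated | Discharge or 7 days |

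Of the four items in footnote 7, two (device-related, procedure-related) depend on relatedness. The other two do not: protocol 16.4 defines sICH by a CT finding plus a worsening of at least 4 NIHSS points, and ENT is named without reference to relatedness.

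**Step 2: test cases**

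1. A RED patient dies in hospital within 7 days. The death is judged stroke progression, without sICH or ENT. It is an SAE under protocol 16.5. It is collected under 7.5.1 sentence 1 and SAP 9, but not under footnote 7 or the list in 7.5.1 sentence 2.
2. A patient not treated with a RED catheter has a serious procedure-related event within 7 days. It is collected under footnote 7 and, as worded, under 7.5.1 sentence 2. It lies outside SAP 9 sentence 1.
3. A RED patient is still in hospital after day 7 and has an unrelated SAE. It is inside the window of 7.5.1 sentence 1 and outside that of footnote 7. SAP 9 can be read either way.

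**Step 3: what SAP 9 tabulates**

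| Event | Explicit n (%) in SAP 9 |
|---|---|
| Serious device-related | Yes |
| Serious procedure-related | Yes |
| Any SAE, regardless of relationship | No |
| sICH at 24 hours | No (named as collected) |
| Symptomatic ENT | No (named as collected) |

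**Step 4: denominator.** Let x be the number of patients with an event when events are collected only in R RED-treated patients, out of N enrolled. The two candidate percentages are x/R and x/N, and x/N = (x/R) × (R/N). The second is smaller by the factor R/N. The documents give N as up to 400 and do not give R, so the factor cannot be evaluated. SAP 7.1 makes all enrolled patients the analysis population, which points to N, while SAP 9 sentence 1 points to R.

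**The case against.** The strongest reply has five parts.

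- **General rules may fill the gap.** SAP 5 prescribes counts and percentages for discrete variables, and SAP 8 promises summaries of measures in the schedule, where SAEs have a row. This stands for sICH and ENT. A reader might infer that no sICH or ENT rate will be produced. The documents do not support that; the rows are only not explicit. The general rule cannot yield an any-SAE rate if sites following footnote 7 did not enter the events.
- **Relationship is already recorded.** SAP 9 lists it, and protocol 16.5 has a grade for unrelated events. This also stands, and it suggests that relationship was meant to be a field. Footnote 7 nevertheless makes it an entry condition for two of its four items, and the listing covers only events that were noted.
- **Other outcomes need no causality call.** SAP 10 names 90-day mortality and discharge NIHSS, and the mRS includes death. So it would be wrong to infer that all safety information depends on causality calls. These outcomes do not count non-fatal SAEs, and the 90-day visit is optional.
- **Two tiers may be intended.** The texts could mean a broad set in RED patients and a narrower list in everyone else. That would be a legitimate design, but no passage states it, and RED patients would still have no any-SAE row.
- **This is a descriptive registry of cleared devices without a safety objective.** That limits the weight of the point. It does not settle which list sites should follow.

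Two further inferences go too far. One is that all four categories in footnote 7 are filtered by attribution; only two are. The other is that relatedness is decided by the sites alone. Protocol 7.5 makes the investigator responsible for reporting and no event review is described, but the assessor of relatedness is not named. Device deficiencies have their own reporting route in protocol 7.5.2, so their absence from SAP 9 is not pressed here.

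**Conclusion.** The point holds as a conflict in collection rules plus an incomplete prespecification. Scope, population and window differ between protocol 7.5.1, Table 1 footnote 7 and SAP 9. SAP 9 gives an explicit count and percentage for two event types, both relatedness-based. It prespecifies no any-SAE rate, has no explicit row for sICH or ENT, and leaves the denominator unstated.

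The effect on reported rates cannot be sized from the documents. It would depend on the SAE rate, the share judged related, the number of RED patients and how many of the up to 30 sites follow each passage, and none of these is given. The conclusion assumes that sites act on the text as written and that no case report form instruction outside these documents already settles the matter. The change should be made, but the registry's objectives on specimens are not affected.

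**What to change.** 1. Reconcile Table 1 footnote 7, both sentences of protocol 7.5.1 and SAP 9 so that one statement governs event scope, population (RED-treated or all) and window. If two tiers are intended, say so and give the list for each. The choice is the sponsor's.
2. For the population in which all SAEs are collected, make relationship to device and procedure a recorded field and not a condition for entry.
3. In SAP 9, add the number and percentage of patients with (a) any SAE regardless of relationship, (b) sICH and (c) symptomatic ENT, beside the two existing rows. State the denominator for every row as the patients in whom that event was collected.

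The cost is reconciled wording, which in the protocol means an amendment with IRB approval, and three more table rows. Sites that followed footnote 7 would have to enter some unattributed SAEs. The any-SAE percentage will be at least as high as either related-event percentage on the same denominator, so the headline safety figure is likely to rise.
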